13.1.1.2 Secondary Evaluations

- The number and percentage of subjects whose corrected serum Ca level was decreased by ≥ 1.0 mg/dL from baseline and remained decreased for 2 weeks in the evaluation period will be calculated, along with the accurate two-sided 95% confidence interval.
- The summary statistics of the actual measured values of corrected serum Ca level and changes from baseline will be calculated for each measurement time point.
- The summary statistics of the actual measured values of intact PTH level and changes from baseline will be calculated for each measurement time point.
- The summary statistics of the actual measured values of whole PTH level and changes from baseline will be calculated for each measurement time point.

13.1.2 Safety Evaluation

The incidence of each adverse event and adverse drug reaction that occurred or worsened after the start of study drug administration will be calculated. Calculation of the incidence of each adverse event and adverse drug reaction will be performed based on the MedDRA PT and SOC.

With regard to laboratory parameters and vital sign values, summary statistics will be calculated for each evaluation time point.

13.1.3 Pharmacokinetic Evaluation

With regard to plasma KHK7580 concentrations, descriptive statistics will be shown for each blood collection time point. Pharmacokinetic parameters (t_{max} and C_{max}) will also be calculated for each subject and descriptive statistics will be provided. In this study, C_{max} is defined as the maximum plasma concentrations at 0.5, 1, 2, and 3 hours after administration, and t_{max} is defined as the time to reach the maximum plasma concentration.

13.1.4 Other Evaluation

The results of the EQ-5D-5L will be tabulated.

13.2 Target Number of Subjects

At least 10 subjects receiving study treatment

For the rationale, see Section 24.10 “Rationale for the Target Number of Subjects.”

13.3 Significance Level Used

A two-sided p -value of 5% will be used as a guide when a test is performed on an exploratory.

13.4 Criteria for Discontinuation of the Study

No study discontinuation criteria based on statistical evidence are provided.

13.5 Procedures for Handling Missing, Rejected, and Abnormal Data

For the analyses specified in Section 13.1, failure to obtain evaluable data for two consecutive weeks regarding the binary response variables for the percentage of subjects in the primary and secondary endpoints will be handled as an “unachieved” subject. Any missing value in continuous data will be handled as missing data, and no special complementary processing by a statistical method will be performed. If any specific handling of the data becomes necessary due to unforeseen events that were not expected at the start of the study, the handling method will be determined before database lock and described in the analysis plan.

13.6 Procedures for Preparing the Analysis Plan and Reporting Deviations from the Original Plan

The details of the final analysis plan, including the analyses shown in Section 13.1, will be finalized as the analysis plan by the time of database lock. Major changes to the analysis plan will be described in the clinical study report.

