3.1.2 Secondary Objective

To evaluate the long-term safety and efficacy of KHK7580 orally administered to patients with hypercalcemia in parathyroid carcinoma or PHPT who are unable to undergo PTx or relapse after PTx

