4 STUDY DESIGN

4.1 Study Design

[figure not shown]
The design of this study is outlined in Table 4.1-1.

This study is a multicenter, intra-subject dose adjustment study. It consists of the screening period (from the time of consent to the start of study drug administration), the evaluation period (up to 24 weeks from the start of study drug administration), and the extended administration period (until Week 52 after the evaluation period).

The investigator or subinvestigator will conduct the screening after obtaining the written consent.

Subsequently, eligible subjects will be enrolled before the start of study drug administration.

Table 4.1-1. Outline of the study design

After enrollment, the date of the start of study treatment (Day 1) will be defined as Week 0, and the subjects will start to receive study drug at the starting dose of 2 mg once daily (daily dose: 2 mg). However, the starting dose may be 2 mg twice daily (daily dose: 4 mg) for subjects with a corrected serum Ca level of > 12.5 mg/dL at screening. Subsequently, the dose level will be adjusted for each subject in accordance with Section 7.1.1 "Dose, Mode of Administration, and Dosing Period" so that corrected serum Ca level can be controlled at ≤ 10.3 mg/dL, and the study drug will be orally administered at each dose level 1 to 4 times daily.

Subjects whose corrected serum Ca level have been maintained at ≤ 10.3 mg/dL for 2 weeks will be transferred to the extended administration period at the time even before Week 24. Other subjects will be transferred to the extended administration period at Week 24 if the investigator or subinvestigator has confirmed that there are no problems with their transfer to the extended administration period. See Table 9.1-1 "Schedule of observation, investigation, and examination (evaluation period)" and Table 9.1-2 "Schedule of observation, investigation, and examination (extended administration period)" for visit schedules for subjects transitioning to the extended administration period before Week 24. The study treatment period will be 52 weeks consisting of the evaluation period and the extended administration period. The time of transition to the extended administration period (starting week of prolongation) will be recorded in the electronic case report form (eCRF). Subjects will be withdrawn from the study at the end of the evaluation period if, at the discretion of the investigator or subinvestigator, they will not be transferred

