12 CRITERIA FOR SUBJECT WITHDRAWAL AND DISCONTINUATION OF THE STUDY, AND PROCEDURES THEREFOR

12.1 Withdrawal of a Subject from the Study

12.1.1 Subject Withdrawal Criteria

A subject will be withdrawn from the study if any of the following conditions apply.

- 1) The subject is found to be ineligible for participation in this study after the start of the study.
- 2) The subject wishes to withdraw the consent for the study.
- 3) It is found not feasible to conduct the necessary observations and examinations due to the subject's private reasons.
- 4) The subject experiences an adverse event, and the investigator or subinvestigator determines that the subject should be withdrawn from the study.
- 5) The subject applied PTx or parathyroid intervention therapy.
- 6) The subject has not taken investigational therapy over 8 weeks.
- 7) The investigator or subinvestigator determines that the subject should be withdrawn from the study.

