13 STATISTICAL ANALYSIS

13.1 Statistical Analysis Methods

The main analytical items for evaluation of efficacy, safety, and pharmacokinetics, as well as the analytical methods, are as follows.

Unless otherwise noted, categorical data will be summarized by frequency and percentage, and continuous data by summary statistics. The summary statistics will involve calculation of the number of subjects, mean, standard deviation, minimum, median, and maximum.

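### The Week 28 to 52 calcium and PTH summaries cover only subjects still under observation, and entry to the extension depends on response, so the long-term efficacy results are open to selection bias

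*Combined protocol and SAP*

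**What the plan says.** **Objective.** Section 3.1.2: "To evaluate the long-term safety and efficacy of KHK7580 orally administered to patients with hypercalcemia in parathyroid carcinoma or PHPT". Section 13.7.1 makes the FAS the population for efficacy.

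**Analyses.** Both binary endpoints in Section 3.2.1 are confined to the evaluation period. What remains for Weeks 28 to 52 is Section 13.1.1.2: "The summary statistics of the actual measured values of corrected serum Ca level and changes from baseline will be calculated for each measurement time point", with parallel wording for intact and whole PTH. Section 13.1 defines the content: "The summary statistics will involve calculation of the number of subjects, mean, standard deviation, minimum, median, and maximum".

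**Missing data.** For continuous variables, Section 13.5 states: "Any missing value in continuous data will be handled as missing data, and no special complementary processing by a statistical method will be performed". For the binary endpoints the same section counts a subject without evaluable data as not having achieved the endpoint.

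**Entry to the extension (Section 4.1).** Subjects who hold corrected calcium at or below 10.3 mg/dL for 2 weeks move across, before Week 24 if they qualify earlier, and no further condition is stated for them. For the rest: "Other subjects will be transferred to the extended administration period at Week 24 if the investigator or subinvestigator has confirmed that there are no problems". The consequence of non-transfer is also given: "Subjects will be withdrawn from the study at the end of the evaluation period if, at the discretion of the investigator". The reason for not entering goes into the eCRF.

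**Later exits.** Section 12.1.1 lists, among others, "The subject applied PTx or parathyroid intervention therapy", more than 8 weeks without study drug, and investigator decision. Section 12.1.2 provides a withdrawal examination and records the date and reason. No regular visits are scheduled after that.

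**The concern.** At each visit from Week 28 the mean is taken over whoever is still in the study, and staying can depend on calcium. One group crosses into the extension because its calcium is controlled. The other crosses only with the investigator's agreement.

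The protocol also gives a subject above target few ways to change calcium treatment while remaining in the study. The dose steps end at level 6 (7.1.1.1), cinacalcet is excluded (7.2.1), the restricted calcium-active drugs may not be started or changed (7.2.2), and parathyroid surgery or intervention ends participation (12.1.1). Seeking other control therefore tends to mean leaving. In parathyroid carcinoma, worsening of the primary disease is not recorded as an adverse event (9.5.1), so the safety tables need not reveal such exits.

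At stake is how the long-term result is read. A mean that stays flat or falls between Weeks 28 and 52 could reflect a lasting effect or the departure of poorly controlled subjects. With a target of at least 10 subjects and no control group described, the planned tables cannot tell these apart.

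**Working it through.** **Inputs from the documents.** N = 10 (13.2, a minimum); efficacy criterion that the exact 95% lower limit exceeds 11% (13.1.1.1); entry above 11.3 mg/dL (6.2) and target 10.3 mg/dL (3.2.1.1). The public text gives no non-transfer rate, no withdrawal rate and no expected calcium values, so everything else below is assumed. There is no plan figure for Weeks 28 to 52 to reproduce.

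**Step 1: a reference case from the plan's own criterion.** The exact lower limit for r of n is the 2.5% quantile of Beta(r, n - r + 1). For 3/10 it is 6.7%, and for 4/10 it is 12.2%. Four responders is the smallest result that meets the 11% criterion at N = 10, so take 4 responders and 6 non-responders.

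**Step 2: formula.** Let responders change by a and non-responders by d, and let k of the 6 non-responders leave.

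- FAS mean = (4a + 6d)/10
- Observed mean = (4a + (6 - k)d)/(10 - k)
- Difference = (a - d) × [4/(10 - k) - 4/10]

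The shift is the gap between the groups multiplied by the change in the responders' share.

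**Step 3: numbers.** Assume a = -1.0 mg/dL (the distance from 11.3 to 10.3) and d = 0, -0.3 or -0.5. At k = 3:

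- d = 0: -4.0/7 = -0.571 against -0.40, shift 0.17
- d = -0.3: -4.9/7 = -0.700 against -0.58, shift 0.12
- d = -0.5: -5.5/7 = -0.786 against -0.70, shift 0.09

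Excess of the observed mean fall over the FAS mean fall (mg/dL):

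| k leaving | d = 0 | d = -0.3 | d = -0.5 |
|---|---|---|---|
| 0 | 0 | 0 | 0 |
| 1 | 0.04 | 0.03 | 0.02 |
| 2 | 0.10 | 0.07 | 0.05 |
| 3 | 0.17 | 0.12 | 0.09 |
| 6 | 0.60 | 0.42 | 0.30 |

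**Step 4: wider gaps.** Take 6 responders at a mean of 10.0 mg/dL and 4 non-responders at 11.5. The full mean is (60 + 46)/10 = 10.60. With 2 non-responders gone it is (60 + 23)/8 = 10.375, about 0.22 lower. With all 4 gone it is 10.0, which is 0.60 lower. With 4 responders at 10.0 and 6 non-responders at 12.5, losing half the non-responders gives 77.5/7 = 11.07 against 11.50, which is 0.43 lower.

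**Step 5: can the direction reverse?** Take one subject at 8.0, five at 10.0 and four at 11.5. The mean is 104/10 = 10.40. Losing only the 8.0 subject gives 96/9 = 10.67. Losing one 11.5 subject gives 92.5/9 = 10.28. Losing both gives 84.5/8 = 10.56. So it can.

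**Step 6: a fixed denominator.** In the reference case, if responders stay controlled and non-responders do not reach target, the FAS share at target is 4/10 = 40% whatever k is. The share among those observed is 4/(10 - k), or 57% at k = 3. The plan reports neither share after Week 24. The comparison shows only that a fixed denominator does not move when non-responders leave.

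**The case against.** A reader might infer that the long-term results are biased in the drug's favour. The documents do not support that as a statement of fact. Transfer is the expected course for the other subjects once the investigator confirms there is no problem, and the text does not define a problem as high calcium; a safety reading is just as natural. Non-transfer could be zero. Eligible patients cannot have parathyroid surgery or have relapsed after it, which may limit exits by that route.

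Nor is selection one-way. Calcium at or below 7.5 mg/dL interrupts treatment (7.1.1.2.4), and more than 8 weeks off drug leads to withdrawal, so low-calcium subjects can leave too. This route is less direct, because treatment may resume once calcium reaches 8.4 mg/dL. At Weeks 6, 10, 14, 18 and 22, regular visits exist only for subjects not yet transferred, so those summaries are selected against the drug. For PTH, any direction assumes in addition that calcium non-responders have higher PTH, and nothing in the documents shows this.

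The two rules in Section 13.5 might also be read as contradicting each other. They do not: scoring a missing result as a failure suits a binary variable and has no direct counterpart for a mean.

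Finally, each summary reports the number of subjects, reasons for leaving are collected, the analysis is descriptive, and the analysis plan stays open until database lock (13.6).

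All of this stands as a limit on certainty and direction. It does not close the gap. A falling n shows neither who left nor what their calcium was. Recording reasons is not an analysis of them. Section 13.5 reserves later decisions on data handling for unforeseen events, whereas non-transfer is written into the design.

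**Conclusion.** The concern holds as a risk. The Week 28 to 52 calcium and PTH summaries are the only planned efficacy analyses for the long-term objective. They are conditional on continuing, and continuing can depend on response. For calcium the likely direction is in the drug's favour if uncontrolled subjects are not transferred or leave later. The bias is zero if all transfer and stay, and withdrawals linked to low calcium could reverse it. For PTH the direction is open.

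In the reference case with 3 of 6 non-responders leaving, the mean fall is overstated by 0.17, 0.12 or 0.09 mg/dL; one exit moves it by only 0.02 to 0.04. Wider assumed gaps between the groups give larger shifts. These figures rest on assumed changes and exit numbers and are not a forecast. The 57% against 40% comparison should not be quoted as an error in a planned result, because no such result is planned.

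The primary endpoint is not affected: it is assessed within the evaluation period, and missing data there count as not achieved. This is a cheap improvement.

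**What to change.** In Section 13.1.1.2, add a supplementary long-term analysis: the number and percentage of the FAS with corrected calcium at or below 10.3 mg/dL at prespecified extension visits (for example Weeks 28, 40 and 52), with the exact 95% confidence interval. Count subjects not transferred, withdrawn or without a value at that visit as not at target. This extends to the long-term data the principle that Section 13.5 already applies to the binary endpoints.

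Keep the observed-case calcium and PTH summaries and label them as conditional on continuing. Show them by evaluation-period response (achieved or not), with the number who left before each visit, the reasons, and their last on-treatment values.

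The cost is some analysis-plan wording and one or two tables. The start week of the extension, reasons for non-transfer, withdrawal reasons and the withdrawal examination are already collected. No visits, subjects or treatment rules change. The downside is a less favourable long-term figure that also counts exits unrelated to calcium as failures; the observed-case table beside it covers this.

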13.7 Selection of Subjects for Analysis

The following populations will be subject to analysis. Whether or not to include individual subjects in each of the analysis populations will be determined prior to database lock if necessary.

13.7.1 FAS

The FAS is defined as the population of the eligible subjects enrolled, excluding those falling under either or both of the following conditions. The FAS will be subject to efficacy evaluation.

- Subjects who have not received any study drug
- Subjects from whom no data of corrected serum Ca levels after the start of study drug administration have been obtained

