12.1.2 Procedure for Withdrawing Subjects

The investigator or subinvestigator will take appropriate measures for a subject who has been withdrawn from the study due to a safety problem such as the occurrence of an adverse event. All subjects who have been withdrawn from the study will undergo withdrawal examination as soon as possible after safety is confirmed.

For subjects who stopped visiting the hospital after study drug administration, follow-up and prespecified assessments will be carried out as much as possible while taking into account the human rights of the subject.

The investigator or subinvestigator will investigate the date of withdrawn and the reason for withdrawal, and enter this information into the eCRF.

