13.1.1 Efficacy Evaluation

13.1.1.1 Primary Evaluation

- The number and percentage of subjects whose corrected serum Ca level was maintained at ≤ 10.3 mg/dL for 2 weeks in the evaluation period will be calculated, along with the exact 95% confidence interval. Whether or not the lower limit of the exact 95% confidence interval exceeds the threshold ratio of 11% will be used as a criterion for judging the efficacy.

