13.7.2 Safety Analysis Set

The safety analysis set is defined as the population of the eligible subjects enrolled, excluding those falling under the following condition.

- Subjects who have not received any study drug

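### Minor: the FAS drops treated subjects with no post-dose corrected serum Ca instead of scoring them 'unachieved', which can only help the primary result

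*Combined protocol and SAP*

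**What the plan says.** - **Section 13.7.1 (FAS).** The FAS is the efficacy population. It starts from eligible enrolled subjects and leaves out those who took no study drug and, separately, "Subjects from whom no data of corrected serum Ca levels after the start of study drug administration have been obtained".
- **Section 13.5.** For the two responder endpoints, "failure to obtain evaluable data for two consecutive weeks regarding the binary response variables for the percentage of subjects" leads to the subject being counted as 'unachieved'.
- **Section 13.7.2.** "The safety analysis set is defined as the population of the eligible subjects enrolled, excluding those falling under the following condition"; the one condition is having received no study drug. This set has the same base population as the FAS without the calcium requirement.
- **Section 13.1.1.1.** The primary result is "The number and percentage of subjects whose corrected serum Ca level was maintained at ≤ 10.3 mg/dL for 2 weeks in the evaluation period", with an exact 95% interval. The efficacy criterion is: "Whether or not the lower limit of the exact 95% confidence interval exceeds the threshold ratio of 11" per cent. Sidedness is not stated here. Section 13.1.1.2 gives the other responder endpoint (a fall of at least 1.0 mg/dL) "along with the accurate two-sided 95% confidence interval".
- **Section 13.2.** The target is "At least 10 subjects receiving study treatment".

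**The concern.** Sections 13.7.1 and 13.5 do not formally conflict: one defines the set and the other scores subjects within it. Together, though, they treat similar subjects differently. A subject lost after a single Week 2 calcium value counts as a failure. A subject lost just before Week 2 leaves the denominator. Neither has shown two weeks of control.

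The subjects removed by the calcium condition are all non-responders, so its effect runs in one direction. In a single-arm trial judged by a lower limit against a fixed threshold, with a target of about 10 subjects, a denominator that can lose only non-responders is undesirable. What could be at stake is a pass that would have been a fail had every eligible treated subject been counted.

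**Working it through.** **Inputs.** Threshold 11% and exact 95% interval (Section 13.1.1.1); target of at least 10 treated (Section 13.2); set definitions (Sections 13.7.1 and 13.7.2); 'unachieved' rule (Section 13.5). Assumption: the interval is two-sided Clopper-Pearson, with 2.5% in the lower tail. 'Treated' below means eligible and treated, because both sets start from eligible subjects. The documents show no expected response rate or power figure to reproduce.

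**Formula.** With x responders among n subjects, the lower limit is L(x, n) = Beta quantile(0.025; x, n − x + 1), and L = 0 when x = 0.

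**Direction.** Let N be treated, of whom k have no post-dose calcium. The FAS analysis uses x/(N − k); scoring the k subjects 'unachieved' uses x/N. The numerator is the same. Over all FAS sizes from 1 to 60, k from 1 to 5 and every possible x (9,450 combinations), neither the rate nor L was ever lower under the exclusion. Both were strictly higher for every x ≥ 1 and both stayed at 0 for x = 0.

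**Responders needed for L > 11%.** 4 at n = 10; 5 at n = 11 to 16; 6 at n = 17 to 21; 7 at n = 22 to 25.

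**Where one exclusion changes the verdict (all x, N from 10 to 25).**

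| Responders | All treated | L | FAS | L |
|---|---|---|---|---|
| 4 | 11 | 10.93% (fail) | 10 | 12.16% (pass) |
| 5 | 17 | 10.31% (fail) | 16 | 11.02% (pass) |
| 6 | 22 | 10.73% (fail) | 21 | 11.28% (pass) |

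Two exclusions add only 4/12 (9.92%), 5/18 (9.69%) and 6/23 (10.23%). With exactly 10 treated, one, two or three exclusions leave the verdict as it was, although the rate and limit still move. The first change needs four: 3/10 (6.67%, fail) becomes 3/6 (11.81%, pass).

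**Chance of passing when the true rate among all treated is 11%.** The documents give no rate of treated subjects without post-dose calcium, so q is assumed. This is an exact trinomial sum (responder 0.11; no post-dose calcium q; other non-responder 0.89 − q), with the second group removed from the denominator.

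| Treated | q = 0 | q = 2% | q = 5% | q = 10% |
|---|---|---|---|---|
| 10 | 0.0178 | 0.0178 | 0.0178 | 0.0181 |
| 11 | 0.0042 | 0.0073 | 0.0113 | 0.0164 |
| 16 | 0.0248 | 0.0248 | 0.0249 | 0.0249 |
| 17 | 0.0075 | 0.0133 | 0.0198 | 0.0262 |
| 22 | 0.0074 | 0.0137 | 0.0198 | 0.0254 |
| 23 | 0.0097 | 0.0110 | 0.0158 | 0.0243 |

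Across all sizes from 10 to 25, it exceeds 0.025 only at q = 10% with 17 or 22 treated.

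**If the limit were one-sided 5%.** One exclusion would change the verdict at 4/14 (10.41% to 11.27%) and 5/19 (10.99% to 11.64%). Two would also change 3/10 (8.73% to 11.11%), 4/15 and 5/20.

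**The case against.** Requiring at least one post-dose value is an explicit, prespecified condition, and the same set also serves the by-time-point calcium and PTH summaries. The trigger is nearly closed by design. Calcium is measured at Week 2 (±4 days), every two weeks after that in the evaluation period, and at discontinuation, and all withdrawn subjects are to have a withdrawal examination (Sections 9.1, 9.4.1.2, 10.3.1 and 12.1.2). At the stated target of 10, up to three exclusions leave the verdict alone. A reader given both set sizes can undo the exclusion by subtraction. Sections 13.5 and 13.7 also leave data handling and set membership to be settled before database lock, and the separate analysis plan may say more.

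Most of this stands, and it is why the point is minor. It does not remove the point:
- For subjects who stop attending, the promise is limited: "For subjects who stopped visiting the hospital after study drug administration, follow-up and prespecified assessments will be carried out as much as possible". Loss before Week 2 remains possible.
- The target is a minimum, so 11 treated is a realistic size, and there one dropped subject can reverse the verdict.
- The by-time-point summaries can keep the calcium condition. The responder endpoints do not need it, because the 'unachieved' score already exists.
- The lock-stage clauses do not prespecify that score for these subjects, and subtraction by a reader does not alter a criterion applied to the FAS.

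One qualification is fair: the safety analysis set is restricted to eligible subjects, so it is not necessarily every subject who took a dose.

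**Conclusion.** The concern holds and is minor. The direction is certain: the exclusion cannot lower the primary response rate or its exact lower limit, and it raises both whenever anyone responds. The size is small. With a two-sided exact interval and 10 to 25 treated, one exclusion reverses the verdict at three counts only, and none of them is at 10 treated. The chance of passing at a true 11% stays below 0.025 if 2% or 5% of subjects lack post-dose calcium, and reaches at most 0.0262 if 10% do. These figures rest on the two-sided reading and on the assumed 2%, 5% and 10%. The direction rests on neither.

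**What to change.** For the primary endpoint and the ≥ 1.0 mg/dL responder endpoint, use the safety analysis set of Section 13.7.2 as the denominator, and state in Section 13.5 that a subject with no post-dose corrected serum Ca is 'unachieved'. Keep the FAS of Section 13.7.1 as a sensitivity analysis for these two endpoints and as the set for the by-time-point calcium and PTH summaries.

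The cost is wording in Sections 13.5 and 13.7.1, with no new data or subjects. The only downside is a slightly less favourable response rate if such a subject occurs.
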